**Exclusion Criteria:**

- Neurodegenerative disease (e.g. Parkinson's, Huntington's, Multiple Sclerosis) other than MCI
- Previous brain lesion
- Intracranial abnormality such as prior stroke
- History of seizure disorder or epilepsy
- A "true" positive response, after patient clarification, to any question on the modified TMS/tDCS Adult Safety Screen questionnaire that would impact patient safety [21] (Refer to **Appendix A**)
- Any history of brain stimulation treatment (e.g., electroconvulsive therapy (ECT), repetitive transcranial magnetic stimulation (rTMS), vagal nerve therapy (VNS), deep brain stimulation (DBS))
- Use of any investigational drug within 4 weeks
- Cardiac pacemakers, implanted medication pumps, intracardiac lines; acute or unstable cardiac disease; intracranial implants (e.g., aneurysm clips, shunts, stimulators, cochlear implants, or electrodes) or any other metal object within or near the head (exception: mouth/dental work) that cannot be safely removed
- Known or suspected pregnancy (extremely unlikely as the age range for this study is 55-85 years)

**Intervention** (independent variable): 5 Day intervention (MCI): Five consecutive weekday tDCS sessions with the Soterix tES system; 1 Day intervention (CU and MCI): 1 tDCS session. Each tDCS session will include cathode electrode placement over the right DLPFC (using the International 10-20 system) at 1.5mA intensity for 15 minutes with anode reference electrode placement over the left DLPFC. The CogState Brief Battery (One Card Learning and One Back Test) is a computerized cognitive battery that will be administered while participants undergo either active or sham tDCS stimulation. Patients who meet the inclusion criteria for the study will be randomized in a 1:1 fashion between sham and active TMS treatment. For this study, we will stratify age in deciles (55-65 years, 66-75 years, 76-85 years), as age is the number one risk factor for neurodegenerative disease. Following randomization, the patients and investigator will be blinded to the treatment group assignment and staff administering treatment will be unblinded. Refer to **Appendix B** for more information regarding device description.

Study Schedule: 5-Day MCI	Pre-Intervention		5 Day Intervention					Follow-Up
	Estimated Time	Screening & Baseline	Day 1	Day 2	Day 3	Day 4	Day 5	1 Month Follow up
Informed Consent	1 hour	x						
Eligibility Checklist 	10 minutes	x						

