Adverse Event Monitoring	5 minutes		x	x	x	x	x	
NIH Toolbox: Cognitive Battery 	30 minutes	x					x 	x
CogState Brief Battery  (Simultaneous with intervention)	15 minutes		x	x	x	x	x	
Intervention: 1.5mA tDCS	15 minutes		x	x	x	x	x	

1. Eligibility checklist includes review of inclusion/exclusion criteria, the modified TMS/tDCS Adult Safety Screen questionnaire, Edinburgh handedness inventory, and PHQ-8 questionnaire

2. NIH Toolbox Cognitive Battery includes: NIH Toolbox Picture Vocabulary Test, Flanker Inhibitory Control and Attention Test, List Sorting Working Memory Test, Dimensional Card Sort Test, Pattern Comparison Processing Speed Test, Picture Sequence Memory Test, Oral Reading Recognition Test

3. NIH Toolbox: Cognitive Battery will be administered 5 minutes after stimulation on Day 5

4. CogState Brief Battery will be administered while active or sham stimulation occurs

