**The study will be performed over 7 sessions for MCI participants in the 5 Day Intervention (Figure 1):**

- **Visit 1 (Screening and Baseline visit):** This will occur ~1-2 weeks before the Five Day Intervention. The purpose of this visit is to obtain informed consent for the study, to screen participants for inclusion and exclusion criteria, and obtain baseline performance of the participant's NIH Toolbox Cognition Battery and CogState Brief Battery (One Card Learning and One Back Test). The TMS/tDCS Adult Safety Screen questionnaire, Edinburgh handedness assessment, and the PHQ-8 will also be administered.
- **Visits 2-6 (Five Day Intervention Days 1-5):** During these visits the participant will receive either active tDCS or sham stimulation. The CogState Brief Battery (One Card Learning and One Back Test) will be administered during stimulation. The visits will take place during a 1-week period (Day 1-5 corresponds to visits 2-6), as five consecutive visits (Monday-Friday). An Adverse Event questionnaire will be administered after each visit. On Visit 5 (last day of intervention), all participants will complete the NIH Toolbox Cognition Battery testing after stimulation.
- **Visit 7 (One month after completion of intervention) follow up visit:** Participants will undergo final NIH Toolbox Cognition Battery. A questionnaire for blind assessment will also be completed.

Study Schedule: 1-Day MCI and CU	Estimated Time	Pre-Intervention	Intervention	Post-Intervention
Informed Consent	1 hour	x		
Eligibility Checklist 	10 minutes	x		
Adverse Event Monitoring	5 minutes		x	
NIH Toolbox: Cognitive Battery 	30 minutes	x		x 
CogState Brief Battery  (Simultaneous with intervention)	15 minutes		x	
Intervention: 1.5mA tDCS	15 minutes		x	

1. Eligibility checklist includes review of inclusion/exclusion criteria, the Montreal Cognitive Assessment (MoCA) >26 (for CU group only), the modified TMS/tDCS Adult Safety Screen questionnaire, Edinburgh handedness inventory, and PHQ-8 questionnaire

2. NIH Toolbox Cognitive Battery includes: NIH Toolbox Picture Vocabulary Test, Flanker Inhibitory Control and Attention Test, List Sorting Working Memory Test, Dimensional Card Sort Test, Pattern Comparison Processing Speed Test, Picture Sequence Memory Test, Oral Reading Recognition Test

3. NIH Toolbox: Cognitive Battery will be administered 5 minutes after stimulation

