4. CogState Brief Battery will be administered while active or sham stimulation occurs

For participants in the 1 day session (MCI and CU) (Figure 2), one visit will include a screening/baseline assessment to screen participants who inclusion and exclusion criteria, and to obtain baseline performance with the NIH Toolbox. The TMS/tDCS Adult Safety Screen questionnaire, Edinburgh handedness assessment, and the PHQ-8 will also be administered, as well as the Montreal Cognitive Assessment (MoCA) >26 for CU participants. Following that, a 15 minute tDCS treatment (active or sham) will be administered and after a rest break, the same assessment using the NIH Toolbox will be repeated. During the tDCS treatment, the participant will do the CogState Brief Battery (One Card Learning and One Back Test). An adverse event questionnaire will be administered after the stimulation.

Risks and Adverse Events: For a full list of risks, see **Appendix C** for more information on anticipated risks. A symptom-based questionnaire will be used to measure adverse events and will be administered at each visit after the screening visit. The frequency and percentage of adverse events will be compared between the 2 treatment arms. Comparisons between arms will be made by using either the Chi-square or the Fisher's exact test.

Safety Evaluation: A literature review showed that all tDCS trials between 1998-2010 [22] showed that of the 209 studies, similar rates in frequency of adverse events in the active vs. sham arms were observed. The most common AE were headache, itching, burning, discomfort and tingling, occurring in 10-40% of patients regardless of treatment group. Refer to **Appendix D** for the Data and Safety Monitoring Plan.

Efficacy Evaluation: The primary outcome measurement is the NIH Toolbox Cognition Battery either at 1 month after intervention (MCI) or after 1 tDCS session (CU and MCI) as compared to baseline scores.

Expected outcomes: We anticipate a change in the NIH Toolbox Cognition Battery scores in the 1-month follow up scores (MCI) or after 1 tDCS session (CU and MCI) as compared to baseline and do not anticipate any change in the sham group.

Statistical analysis: Continuous variables will be summarized as a mean  $\pm$  SD or median. Categorical variables will be summarized using number and percentage. Univariate descriptive statistics and frequency distributions

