#### 1. Participant Safety

- a) Safety will be monitored by the Investigator and study team
- b) Participants will be seen by an appropriately trained health professional at every visit and the evaluation will be documented.
- c) Participants will be monitored for adverse events (AEs) throughout every visit.

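### The text requires the adverse-event questionnaire at every visit after screening, but the 5-day schedule and the Visit 7 description leave it out at 1 month, so events after Day 5 may be missed

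*Combined protocol and SAP*

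**What the plan says.** Four places in the combined protocol and SAP bear on this point.

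- **Risks and Adverse Events.** The rule is general: the symptom questionnaire "will be administered at each visit after the screening visit". The same paragraph plans to compare adverse events between the two arms by Chi-square or Fisher's exact test. It gives no start or end of the collection period.
- **Study Schedule: 5-Day MCI.** The row "Adverse Event Monitoring" has a mark under each of Days 1 to 5 and none under "1 Month Follow up".
- **Visit descriptions for the 5-day cohort.** For Visits 2 to 6 the text says "An Adverse Event questionnaire will be administered after each visit". For Visit 7 it says "Participants will undergo final NIH Toolbox Cognition Battery" and adds a questionnaire on blinding. It does not mention adverse events.
- **Section 1, Participant Safety, of the safety monitoring plan.** "Participants will be monitored for adverse events (AEs) throughout every visit". No instrument is named.

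**The concern.** The general rule and the operational instructions disagree about one visit. A coordinator who prepares Visit 7 from the schedule table or from the visit description would not bring the questionnaire. One who reads the Risks and Adverse Events paragraph would.

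At stake is what enters the safety comparison. That comparison has no stated window, so the events counted depend on which part of the document the staff followed. If practice varied between participants, some would contribute counts from the stimulation week alone and others from the week plus the month after it. Visit 7 is also the only scheduled contact after Day 5, and so the only planned occasion to ask systematically about delayed or persisting symptoms. The 5-day cohort is the only one with repeated stimulation. Appendix C lists effects that may follow treatment, among them headache including migraine and dizziness, and it also provides for severe depression arising during the trial. The PHQ-8 is scheduled at screening only, so it would not fill the gap.

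**Working it through.** The plan states no figure to reproduce here. The check is a comparison of the relevant places and a count of visits.

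**Inputs**

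- Visits in the 5-day cohort: "The study will be performed over 7 sessions for MCI participants in the 5 Day Intervention", made up of 1 screening and baseline visit, 5 stimulation visits and 1 follow-up visit. The plan equates Days 1 to 5 with Visits 2 to 6.
- Participants: 44 in the 5-day MCI cohort (22 per arm), 44 in the 1-day CU cohort and 44 in the 1-day MCI cohort (synopsis; Power and Sample Size Calculation).
- Time allotted to adverse-event monitoring: 5 minutes (schedule table).

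**Step 1. Could the empty cell be a loss in the conversion from PDF?** The NIH Toolbox row of the same table does carry a mark at 1 month, so the column is intact. The prose for Visit 7 leaves the questionnaire out independently. The omission is in the plan.

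**Step 2. Administrations per participant.**

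- Text rule: 7 visits − 1 screening visit = 6 (Visits 2 to 7).
- Schedule and visit descriptions: 5 (Visits 2 to 6).
- Difference: 6 − 5 = 1, which is Visit 7; 1/6 ≈ 17% of the required administrations.

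**Step 3. Participants affected.** Planned total: 44 + 44 + 44 = 132. The discrepancy touches 44 of 132, or one third. The 1-day cohorts have no later visit, and both their schedule and their description call for adverse-event collection with the single stimulation session.

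**Step 4. Administrations lost if the schedule is followed throughout.** With all 44 attending every visit, 44 × 1 = 44 of 44 × 6 = 264. If only the 19 per arm that the plan expects to retain reach Visit 7, 38 are lost.

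**Step 5. Events lost.** This would need a rate of events arising or persisting after Day 5. The documents give none, so no number follows.

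**The case against.** The strongest reply is that the plan already calls for collection at 1 month. The rule stands in the same paragraph as the arm comparison, so the comparison as written includes Visit 7. The safety monitoring plan has a trained health professional see each participant at every visit, document the assessment and watch for adverse events. Appendix C has symptomatic interventions entered in the case file, and the IRB reporting route has no cut-off at Day 5. Appendix C also describes the commonest effects as short-lived, so the yield at 1 month may be small. The primary outcome is untouched.

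Much of this stands. A reader might infer that events after Day 5 will go uncounted. The documents do not support that: the loss is conditional on staff following the schedule, and an event could still be noted at Visit 7 without the questionnaire.

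A reader might also express the gap as calendar time. If the month is taken as 28 days, with 4 days from Day 1 to Day 5, then 28/(4 + 28) = 28/32 = 87.5% of the period would have no questionnaire. That is a share of days under an assumed month length. It is not a share of events, which the plan expects to cluster around stimulation.

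The reply does not remove the contradiction. The monitoring statement names no instrument, speaks of monitoring during visits and not of asking about the preceding month, and does not say that events noted in this way enter the arm comparison. Events elicited by a symptom questionnaire on Days 1 to 5 and events noted incidentally at Visit 7 are not the same measurement.

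**Conclusion.** The concern holds as an internal inconsistency with a conditional consequence. The plan's own rule requires six questionnaire administrations in the 5-day cohort, and its schedule and visit descriptions provide for five. If staff follow the schedule, the missing one is Visit 7 for all 44 participants, and delayed or persisting events may be missed in the active-versus-sham comparison.

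The count rests on the plan's visit structure alone; the totals in Step 4 also assume attendance as stated there. The effect on adverse-event counts cannot be given, because the documents contain no late-event rate. The point does not bear on the NIH Toolbox outcome or on the 1-day cohorts. It goes beyond a clerical slip because it decides which data enter a planned comparison, and because following the table would break the plan's own rule for collecting safety data.

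**What to change.** Reconcile the four places as follows.

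1. In the 5-day schedule, mark adverse-event monitoring in the 1-month follow-up column.
2. In the Visit 7 description, add the symptom questionnaire and have it ask about events since Day 5.
3. In the Risks and Adverse Events paragraph, state that the arm comparison covers all visits after screening. One stated window is enough; nothing in the plan requires a second comparison restricted to the stimulation days.
4. In section 1 of the safety monitoring plan, refer to the same questionnaire, so that monitoring at each visit and the data behind the comparison are tied together.

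The cost is a correction to one table and a few sentences, plus about 5 minutes per participant (the schedule's own allowance) at a visit that already takes place. Sample size and the efficacy analysis are unchanged.

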### Other potential side effects that may be experienced *following* rTMS treatment

Transient redness under the electrode, local pain, headache including migraine, transient dizziness, brief changes in attention and thinking). **Severe depression:** If a participant states they are severely depressed during the trial, we will promptly refer them to Arizona’s Psychiatry and Psychology department. This will be facilitated through [name] (PI) and [name], who are members of the department of psychiatry and psychology and part of the research team.

Treatment plan for other potential side effects experienced *following* treatment:

Participants reporting headaches during or following study treatment will be encouraged to take acetaminophen or ibuprofen prior to the daily treatment. All patients will be monitored, and appropriate treatment will be recommended including the possibility of stopping tDCS. All symptomatic interventions will be recorded in participant's case file.

Device-Related Adverse Event

A device related adverse event is defined as any adverse event for which, at least, a reasonable possibility exists between the event and the investigational device (e.g., the relationship between the device and event cannot be ruled out).

Device Failure, Malfunctions and Near Incidents

Investigators will report all possible device failures, malfunctions or near incidents observed during the course of the trial. These incidents will be documented as follows:

**Device Failure:** A device failure has occurred when the device is used in compliance with the study protocol, but does not perform as described in device manual and also negatively impacts treatment of the study participant.

**Device Malfunction:** A device malfunction occurs when an unexpected change to the device that is contradictory to the device manual is observed, which may or may not affect device performance.

**Device Misuse:** Any use of the investigational device by an investigator that is contradictory to the application described in the study protocol will be categorized as device misuse.

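### The symptom questionnaire is first given after stimulation, so pre-existing headache, dizziness or thinking complaints can be counted as adverse events and dilute the active-sham comparison

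*Combined protocol and SAP*

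**What the plan says.** Under Risks and Adverse Events the protocol names the instrument: "A symptom-based questionnaire will be used to measure adverse events". It is to be "administered at each visit after the screening visit". The analysis follows: "The frequency and percentage of adverse events will be compared between the 2 treatment arms", by chi-square or Fisher's exact test.

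The cohort descriptions agree that nothing is collected before exposure:

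- **5-day MCI cohort.** For Visits 2 to 6, "An Adverse Event questionnaire will be administered after each visit". In the 5-day schedule the row "Adverse Event Monitoring" is marked on Days 1 to 5 and is empty at Screening & Baseline.
- **1-day CU and MCI cohorts.** "An adverse event questionnaire will be administered after the stimulation". The schedule marks the intervention column only, so the form is used once, after the only session.

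Appendix C lists possible effects after treatment, among them "headache including migraine, transient dizziness, brief changes in attention and thinking". The only adverse-event definition in the text available is that of a device-related event. It asks for a reasonable possibility of a link and gives as an example that "the relationship between the device and event cannot be ruled out". No passage limits an adverse event to a symptom that is new or worse than before treatment.

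**The concern.** Headache, dizziness and complaints about thinking occur without stimulation, and two of the three cohorts are enrolled because of cognitive impairment. A form first completed after stimulation cannot by itself separate a symptom that began with treatment from one that was there that morning. In the 5-day cohort the later forms cannot stand in for a baseline, since each follows a session.

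Two things are at stake. A real active-sham difference in these symptoms becomes harder to see. The absolute rates in both arms can also be too high, which matters because the protocol's feasibility paragraph says the pilot is meant to supply data for grant applications. The plan adjusts for baseline when it analyses the NIH Toolbox scores, but has no counterpart for symptoms.

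**Working it through.** **Inputs from the protocol.** 22 per arm in each cohort and 1:1 allocation (Power and Sample Size Calculation; Intervention); two-sided 0.05 (Statistical analysis); Fisher's exact test (Risks and Adverse Events). A review cited under Safety Evaluation puts common events at 10-40% of patients regardless of group. Appendix C gives headache as 14.8% on active tDCS and reports no active-sham difference in event rates. The protocol states no expected difference, background rate or power for the adverse-event comparison, so there is no figure of its own to reproduce. Its sample size was set for efficacy.

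**Assumptions.** True treatment-period rates t_A (active) and t_S (sham), and a background share b that is equal in both arms and independent of treatment. No dropout.

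**Formulas.**
- As planned, every reported symptom counts: observed rate = b + (1-b)t. The arm difference is (1-b)(t_A - t_S).
- With a baseline, only new symptoms count and all 22 stay in the denominator: observed rate = (1-b)t. People who already have the symptom cannot become cases.
- Power is the sum of the binomial probabilities of all 23 x 23 possible tables for which the two-sided Fisher p-value is below 0.05.

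**Example: 30% v 5%, b = 20%.**
- As planned: 0.20 + 0.80 x 0.30 = 44% and 0.20 + 0.80 x 0.05 = 24%. The difference falls from 25 to 20 points and the risk ratio from 6 to 44/24 = 1.8.
- With a baseline: 0.80 x 0.30 = 24% and 0.80 x 0.05 = 4%.

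The difference is 20 points under both definitions. The gain comes from removing noise. The standard error of the difference is sqrt[(0.44 x 0.56 + 0.24 x 0.76)/22] = 0.140 as planned and sqrt[(0.24 x 0.76 + 0.04 x 0.96)/22] = 0.100 with a baseline.

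**Exact Fisher power, 22 per arm, b = 20%.**

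| True rates, active v sham | Observed as planned | Power as planned | New symptoms only | Power with baseline |
|---|---|---|---|---|
| 30% v 5% | 44% v 24% | 19% | 24% v 4% | 37% |
| 40% v 10% | 52% v 28% | 25% | 32% v 8% | 41% |
| 30% v 10% | 44% v 28% | 12% | 24% v 8% | 20% |
| 14.8% v 5% | 31.8% v 24% | 4.8% | 11.8% v 4% | 4.9% |

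**Other background rates.**
- For 30% v 5%, power is 51% with no background. It is 29% v 44% (planned v baseline) at b = 10% and 13% v 29% at b = 30%.
- For 14.8% v 5%, it is 6.5% v 6.6% at b = 10% and 3.8% v 3.4% at b = 30%, so there the baseline gains nothing.

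The model counts new symptoms only. Counting worsened ones as well would add cases among people who had the symptom at baseline; that was not modelled.

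**The case against.** The strongest reply is that the comparison is randomised and sham-controlled. The sham arm shows the background rate, no power is claimed for adverse events, and this is a feasibility pilot. That stands as far as bias is concerned: a reader might infer that the arm comparison is biased, and on average it is not. It does not answer dilution, nor inflated absolute rates.

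Four further readings go beyond the documents:

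- **That pre-existing symptoms will be counted.** The questionnaire's wording and any attribution rule are not shown. It may ask only about symptoms during or since stimulation. The supportable claim is that they can be counted.
- **That a change in attention or thinking cannot be identified at all.** The NIH Toolbox, which includes a test of attention, is given before and after stimulation in every cohort. It does not feed the adverse-event comparison and does not record subjective complaints, but it is a before reading.
- **That nothing about earlier symptoms is recorded, or that long-standing complaints are device-related by definition.** The safety screen in Appendix A has a yes/no headache item, and a yes must be followed up. Appendix C speaks of dizziness that is transient and changes that are brief, and its definition requires a reasonable possibility of a link. These inform attribution but do not give symptom status on the day of treatment.
- **That the gain is large because the three cohorts can be pooled.** At 66 per arm (3 x 22), 30% v 5% with 20% background gives 63% v 91%. The protocol refers only to two treatment arms and states no pooling, so this figure is not relied on.

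It also stands that the commonest effects listed in Appendix C, such as scalp itching, tingling and burning, probably have little background. The point concerns mainly headache, dizziness and thinking complaints.

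**Conclusion.** The point holds as a cheap improvement, not as a flaw that invalidates the safety comparison. In every cohort the instrument that measures adverse events is first used after exposure, and no visible rule restricts the count to new or worsened symptoms. Background symptoms can therefore raise both arms' rates and shrink a true difference by the factor (1-b).

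The size rests wholly on assumed rates. With 20% background, a baseline adds between nothing and about 18 percentage points of power in the scenarios tried. The top of that range needs a large effect on a symptom that is also common beforehand. At the headache rate the protocol cites, against an assumed 5% on sham, there is no gain. Even the best case with 20% background reaches only 41%, so the missing baseline worsens a limit set by 22 per arm rather than creating it.

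**What to change.** - Give the same questionnaire once before the first stimulation: at Visit 1 or before the Day 1 session in the 5-day cohort, and before the single session in the 1-day cohorts. Mark it in both schedule tables.
- In Risks and Adverse Events, define the compared event as a symptom that is new or worse than on that form, compare arms on it, and tabulate all reported symptoms alongside.
- While editing, reconcile the general timing rule with the 5-day schedule. Read literally, the rule covers the 1-month visit, where the adverse-event row is empty.

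The cost is one more use of a 5-minute form per participant, at a contact that already takes place, and one definition in the analysis. Asking beforehand may prompt some later reports, but equally in both arms. Visits, treatment and sample size do not change. The baseline cannot be reliably recovered once stimulation has begun.
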